2. OBJECTIVES

Primary Objective:

- Gathering data on self-measured blood pressure and AF detection of patients using the Stroke Box as a basis for power analysis of a future randomized controlled clinical trial and performing a quality assessment of the collected data.

Secondary Objectives:

- Gathering data on self-measured heart rhythm, weight and activity of patients using the Stroke Box, and performing a quality assessment of the collected data.
- Evaluation of the potential change in self-management, patient engagement and user experience of the patients using the Stroke Box, using questionnaires.
- Assessment of patient adherence to the self-measurements and pharmacotherapeutic prophylactic therapy, using questionnaires.
- To evaluate our implementation of the IT infrastructure, hardware and LUMC Care app, and to assess the correct use of all stakeholders involved in the eHealth support and telemonitoring with the Stroke Box. The devices themselves and their functioning are not a subject of research.
- User based evaluation of the technical – and workflow implementation for healthcare professionals using the Stroke Box, using questionnaires.

3. STUDY DESIGN

In this pilot study we will evaluate the technical feasibility and clinical implementation of the Stroke Box in a small prospective cohort. After providing the Stroke Box to the patients, detailed information will be provided on the use of the Stroke Box and the patient will be helped with their first use.

The patient will use the Stroke Box to take at-home measurements for six months. Here we will be gathering data on blood pressure management, cardiac rhythm, patient engagement and have a user-based evaluation of the eHealth infrastructure. Patients will perform regular home measurements which the GP can use at the regular visits, and a nurse specialist in the LUMC will assess ECG measurements. We will keep close contact with both patient and GP to help in case of any questions. The patients will have access to the LUMC Box Support helpdesk who are an established customer service desk to help with any Box-related issues. We will ask the patients and GPs to contact us in case of any questions they might have. At the end of the pilot the user evaluation will be done through a questionnaire.

During the regular GP visits after the stroke related hospital admission, the GP and the nurse specialist will have insight in the collected data. We will evaluate the GP's experience of the data insight and technical usability using a questionnaire.

The study is estimated to take 12 months where we will have 6 months of inclusions and 6 months of follow-up.

4. STUDY POPULATION

4.1 Population (base)

We will recruit patients visiting for a TIA or admitted for an ischemic or haemorrhagic stroke in the LUMC.

4.2 Inclusion criteria

In order to be eligible to participate in this study, a subject must meet all of the following criteria:

- The patient is admitted with a clinical diagnosis of a TIA, ischemic or haemorrhagic stroke in the LUMC
- The patient is able to communicate in Dutch (patients with severe aphasia - defined as not being able to respond to the questionnaires or perform the self-measurements – are excluded)
- The patient is at least 18 years of age
- The patient will be discharged from the hospital directly to home
- The patient has hypertension during hospital admission as defined by systolic blood pressure >140mmHg during two separate blood pressure measurements
- The patient has a suitable smartphone and is able to use it in a reasonable sense
- The GP of the patient is willing to collaborate in the study

4.3 Exclusion criteria

A potential subject who meets any of the following criteria will be excluded from participation in this study:

- The patient does not have internet access at home
- Patient is unwilling to sign the informed consent form
- Patient is considered an incapacitated adult
- The patient is a pregnant or breastfeeding woman
- The GP of the patient is not willing to partake in the study

4.4 Sample size calculation

In the LUMC there are 450 stroke patients per year, 50-60% of which are immediately discharged home. Of these patients we expect 85% willing to sign the informed consent form and have the GP willing to cooperate in the pilot. We will be including patients for a maximum of 6 months, in this time there will be about 105 potential patients for our study according to our calculations. We will be including 55 patients. We will use this patient population to estimate incidence of blood pressure out of the therapeutic window (>140mmHg) for the power analysis of a future clinical trial.

In 37.5% of patients, we expect to see a change in blood pressure in 6 months,¹⁴ this would amount to 20 patients in our population of 55 patients. This would be sufficient to power a future trial focusing on blood pressure measurements using the Stroke Box infrastructure. Earlier studies focussing on long term recording of heart rhythm in patients with cryptogenic stroke found occult atrial fibrillation in 9% to 16% of patients.^{3,15} As 87% of stroke patients have ischemic strokes¹⁶ and about a third of those have cryptogenic strokes, we expect to find cryptogenic strokes in about 29% of the LUMC stroke population.¹⁷ Therefore, we expect around two to three patients in which we would detect atrial fibrillation after hospital discharge. This would be the minimum to power a future trial focussing on atrial fibrillation detection using the ECG smartwatch. In conclusion, 55 patients amounts to the minimum size we would need to obtain sufficient results.

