When the patient records abnormal measurements indicating a high or rapid increase in blood pressure, they are instructed to not immediately contact a physician. This, in order to reduce the amount of (unnecessary) additional consults with the GP. Specifically, the patient is instructed to only contact their GP if they record a systolic blood pressure >140 mmHg for three days in a row or take up immediate contact if they record a systolic blood pressure >180 mmHg which is cause for immediate adjustment of the hypertension medication according to the NHG guidelines.

In addition to the standard care where patients receive a 48-hour Holter, patients who are suspected to have atrial fibrillation because of e.g. a cryptogenic stroke will be asked to also perform home measurements of their heart rhythm on a daily basis. They are recommended to do this on the same day and time every day. They will be very clearly instructed that their ECG measurements are not monitored regularly and that they should contact 112 in case of emergency.

After a measurement the Withings Move ECG performs a standard analysis resulting in either "normal", "inconclusive" or "atrial fibrillation". If their ECG smartwatch shows "atrial fibrillation" they are instructed to contact a dedicated nurse specialist who will check the measurements and refer them to the cardiology outpatient clinic if necessary. If the result is "inconclusive", the patient is asked to repeat the measurement the next day. When the repeated measurement shows "inconclusive" again or when the measurement shows a warning for potential AF, they are instructed to also contact the dedicated nurse specialist who will contact the patient for further follow-up if necessary. It should be noted that a clinical diagnosis will never be based on the self-measurements. Instead they serve as an early screening tool leading to patients with potential AF to be invited to the cardiology outpatient clinic to receive a diagnosis via the standard Holter measurement.

All ECG data are collected after the study and re-inspected by a PhD researcher of the LUMC for AF and in case of doubt checked again by an experienced cardiologist. In case of suspected AF, the patient is invited to the cardiology outpatient clinic. As 87% of stroke patients have ischemic strokes¹⁶ and about a

third of those have cryptogenic strokes, we expect to find cryptogenic strokes in about 29% of the LUMC stroke population.¹⁷

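### The expected AF count in section 4.4 is optimistic for the cryptogenic subset: a yield from long-term rhythm recording is applied unadjusted to self-taken spot ECGs, and the plan's own inputs give 1.4 to 2.6, not two to three

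*Combined protocol and SAP*

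**What the plan says.** Section 4.4 builds the AF projection in three steps. It starts from the sample: "We will be including 55 patients". It derives a cryptogenic share from two proportions, that "87% of stroke patients have ischemic strokes" and that "about a third of those have cryptogenic strokes", and concludes that "we expect to find cryptogenic strokes in about 29% of the LUMC stroke population". It then brings in the yield: "Earlier studies focussing on long term recording of heart rhythm in patients with cryptogenic stroke found occult atrial fibrillation in 9% to 16" per cent of patients. The result is that "we expect around two to three patients in which we would detect atrial fibrillation after hospital discharge", followed by this use of the count: "This would be the minimum to power a future trial focussing on atrial fibrillation detection using the ECG smartwatch". The section closes by calling 55 the minimum size needed.

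The rhythm sampling in the pilot is described elsewhere, in two ways. Section 8.3 asks patients suspected of AF, with cryptogenic stroke given as an example, to take a home ECG daily, and on timing says "They are recommended to do this on the same day and time every day". The summary (intervention, and burden and risks) describes weekly measurement, including heart rhythm, for patients in general. Neither place gives a detection rate for such recordings relative to long-term recording, and no expected adherence or dropout rate is stated.

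**The concern.** The borrowed yield and the pilot's detection method are different kinds of measurement. A yield from long-term recording reflects how much rhythm was observed. A self-taken spot ECG shows intermittent AF only if an episode is under way when the patient records, and only if the patient does record. Section 4.4 carries the yield through with an implied capture of 100%.

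This matters for two reasons. First, the count is part of the argument for 55 patients: it is declared the minimum for a future AF trial, which leaves no margin for any loss. Second, section 2 names AF detection in the primary objective as a basis for the future power analysis. Unless the expected loss is acknowledged and the recordings actually made are reported next to the yield, a low or zero pilot count cannot be interpreted. Few AF cases, sparse sampling and poor adherence would all look the same.

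**Working it through.** **Inputs from section 4.4:** N = 55; ischaemic share 0.87; cryptogenic share of those about 1/3; AF yield 0.09 to 0.16.

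**Reproducing the plan's figure.**
- Cryptogenic share: 0.87 × 1/3 = 0.29.
- Cryptogenic patients: 55 × 0.29 = 15.95.
- Expected AF: 15.95 × 0.09 = 1.44; 15.95 × 0.16 = 2.55.

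Ordinary rounding gives 1 to 3. The stated two to three needs the low end rounded up. Expecting exactly two requires a yield of 2/15.95 = 12.5%. Expecting exactly three requires 3/15.95 = 18.8%, above the quoted 16%. Applying the yield to all 55 patients would give 4.95 to 8.80, so the plan clearly meant the cryptogenic subset only.

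**Variability at full capture.** Treat each of the 55 as having probability p = 0.29 × yield of being a cryptogenic patient with detected AF, independently and with complete follow-up. Then P(fewer than 2) = (1 − p)^55 + 55p(1 − p)^54.
- Yield 9%: p = 0.0261; 0.23 + 0.34 ≈ 0.58 (unrounded terms).
- Yield 16%: p = 0.0464; 0.07 + 0.20 = 0.27.

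**Adding a capture term.** Let s be the share of the long-term-recording yield that spot ECGs would find. The documents give no value for s, so the rows below 100% are assumptions for illustration. Expected count = 15.95 × yield × s, and the probabilities use p = 0.29 × yield × s.

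| Assumed s | Expected count (9% to 16% yield) | P(none) | P(fewer than 2) |
|---|---|---|---|
| 100% | 1.44 to 2.55 | 23% to 7% | 58% to 27% |
| 75% | 1.08 to 1.91 | 34% to 14% | 71% to 43% |
| 50% | 0.72 to 1.28 | 49% to 27% | 84% to 63% |
| 25% | 0.36 to 0.64 | 70% to 53% | 95% to 87% |

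**What the count leaves out.** The other 55 − 15.95 = 39.05 patients contribute nothing to the projection. At s = 50%, the yield among them that would bring the total back to two is (2 − 1.28)/39.05 = 1.9% to (2 − 0.72)/39.05 = 3.3%.

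**The case against.** A reader might infer that two to three, or 1.4 to 2.6, is an upper bound on what the pilot can find. The documents do not support that.
- The projection covers cryptogenic strokes only. Section 8.3 offers the daily ECG to anyone suspected of AF, and the summary has patients in general measuring rhythm. As shown above, a yield of about 2–3% in the remaining patients would restore a total of two at 50% capture.
- The duration of the cited recordings is not given, nor are they described as continuous. Recordings shorter than six months could have missed AF that arises during this pilot's follow-up.
- Section 6.4 does not exclude false positives from the watch.
- 1.4–2.6 is an expectation. At full yield, three or more detections still have a 17–47% chance.

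A reader might also infer that recording at a fixed time of day makes the loss worse. With episodes starting at random times, a fixed and a varying daily time capture equally well. A fixed time matters only if AF follows the clock, which the documents do not say, and section 8.3 only recommends the timing.

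The plan can also be defended on use. Section 2 already makes Stroke Box data the basis for the future power analysis, so nothing shows that 9–16% will be carried into the next trial. Section 10.1 already summarises weekly measurement frequency, section 8.1.2 already assesses regularity and measurement error, and section 8.3 has all ECGs re-inspected. The summary and section 8.1.1 state the primary objective in terms of blood pressure alone, section 8.1.2 lists heart rhythm as secondary, and the analysis is descriptive with no AF threshold to fail.

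All of this stands and limits the point. It does not justify applying a long-term-recording yield to spot ECGs without comment, nor resting a minimum-size statement on the result. Section 4.4 does not rely on detections outside the cryptogenic subset.

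**Conclusion.** The point holds in a limited form. For the cryptogenic subset, the section 4.4 count is optimistic because it allows nothing for intermittent self-recording or adherence. The documents do not let one derive the size of that loss, and 0.7–1.3 expected detections is only an illustration at an assumed 50% capture.

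One part needs no outside assumption about capture. The plan's own inputs give 1.4–2.6, and a count below the two-patient low end has a 27–58% chance even at full capture. Those probabilities assume independent patients and complete follow-up. The claim that this count is the minimum to power a future trial therefore has no margin behind it.

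The conflict between daily and weekly ECGs adds to the uncertainty: until it is settled, no yield can be projected for the schedule actually used. The matter is worth correcting before the results are used for planning. It does not affect recruitment or the blood pressure objective.

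**What to change.** 1. In section 4.4, restate the AF figure as about 1.4–2.6 expected in the cryptogenic subset if spot recording detected as much AF as long-term recording, and fewer if it does not (for example 0.7–1.3 at an assumed 50% capture, labelled as an assumption).
2. Add that detections in other patients suspected of AF are not included in this count.
3. Remove or qualify the statement that the count is the minimum to power a future AF trial, and adjust the closing sentence on 55 patients to match.
4. Reconcile the ECG schedules in section 8.3 (daily, patients suspected of AF) and the summary (weekly, patients in general) before projecting any yield.
5. In section 10, report the pilot AF yield together with the number of readable recordings and recording days per patient, so that a low or zero count can be interpreted.

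The cost is a rewritten paragraph, one consistency correction and one table from recordings that are already uploaded and re-inspected. The stated AF expectation becomes less favourable. No patients or procedures are added.

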5. TREATMENT OF SUBJECTS

5.1 Investigational product/treatment

Patients receive the Stroke Box containing several monitoring devices. The Stroke Box uses a dedicated app, the LUMCcare app. A list of devices is presented below and described in more detail in section 6 of this protocol. All devices and products are CE-marked and used within the scope of their intended use in this certification.

The devices within The LUMC Box are connected to the LUMCcare app. All measurements performed by the patient with the connected devices will be automatically uploaded into the LUMCcare app, and safely transferred to the hospital for evaluation. Furthermore, illness specific questionnaires are presented within the app at the appropriate time points.

The Stroke Box contains the following devices and products:

- Withings BPM connect
- Withings Body Weight Scale
- Withings Move ECG Watch
- LUMCcare app
- Withings Health Mate app
- IkOefenZelf access (for 10 patients only)
- StopAdvisor app access

5.2 Use of co-intervention (if applicable)

Not applicable.

5.3 Escape medication (if applicable)

Not applicable.

6. INVESTIGATIONAL PRODUCT

6.1 Name and description of investigational product(s)

Withings Body Weight Scale

The Withings body weight scale is a CE-marked Bluetooth enabled weight scale which measures weight, body fat mass, heart rate and the CO₂ ppm in the air. It sends the results to the LUMCcare app. The Withings Weight Scale is battery powered, CE-marked and electrically safe. In order to measure weight, patients have to stand on the weight scale. Data are automatically sent to the smartphone via Bluetooth.

Withings BPM Connect

The Withings BPM Connect Blood Pressure Monitor is a CE-marked, Bluetooth enabled blood pressure cuff which can be placed around the upper arm of the patients. The inflation and deflation of the cuff will lead to a systolic and diastolic blood pressure, as well as a heart rate, which are shown on the device itself and in the LUMCcare app on the smartphone. The Withings BPM Connect Blood Pressure Monitor is battery powered and electrically safe. It is CE-marked for blood pressure measurement. A previously published study that showed that median values are within the 5 mmHg range.¹⁸

Withings Move ECG Watch

The Withings Move ECG Watch is a wearable, CE-marked, Bluetooth enabled smart watch. The wristwatch combines single lead ECG measurements with activity tracking such as walking, running, swimming and many other activities and workouts. It measures steps, distance and calories consumed and sends all its results to the LUMCcare app via Bluetooth. The Withings Move ECG Watch is battery powered and electrically safe.

LUMCcare app

Data are presented on the LUMCcare app. The data resides within the Withings Health Mate connection app on the smartphone in encrypted form. The Withings Health Mate connection app initial logon will require several privacy-related patient data: full name and date of birth. This procedure complies with the LUMC requirements and has been approved by the LUMC security officer. For the Withings connection app, an integration (API) in the Electronic Medical Record (EMR, EPD-Vision) has been built. This API has been functional for 6 years already. Physicians and specialized nurses can thus evaluate the e-Health measurements of the patients in the EMR.

The LUMCcare app presents the data to the patient in an intuitive interface. The app is co-created with Pharos, the advocate group for people with low literacy, in order to ascertain the measurements are understandable for a large group of patients. The app reminds

patients to take measurements based on the protocol prescribed by the health care provider. It allows patients to fill in questionnaires at appropriate time points. The app communicates with the LUMC infrastructure according to LUMC guidelines and is approved by the LUMC security officer. As for how to use the app, patients will receive oral and written instructions. If they run into problems, a helpdesk is available, which is run by an LUMC employed technician.

Withings Health Mate app

The Withings3 Health Mate connection app requires a user specific account, that is accessed using a hospital-provided, coded username and a password. The account cannot be linked to an individual patient. This procedure complies with the LUMC requirements and has been approved by the LUMC security officer. For retrieving the data from the Withings Health Mate app, the LUMC uses an API connection, which unlocks the patient measurement data. This API has been functional for 6 years already. Authorized users can thus evaluate the e-Health measurements of the patients in the electronic patient file.

Data is securely shared with the GP office via Medical Dashboard, an dedicated information portal that allows GPs to assess specific data from the LUMC. The Medical Dashboard is operational at the LUMC for already 8 years and complies with the LUMC requirements and has been approved by the LUMC security officer. Over the course of the next years, the underlying technology will be updated to new technology, in line with the established roadmap of the It&DI department of the LUMC. This effort is currently underway and may result in selection of a novel target architecture for regional connectivity in the coming period. All efforts will be taken to ensure this study protocol can continue also during implementation of novel architectures.

In addition to this, the Health Mate app also gives the patient insight into his/her measurements. Moreover, when the Move ECG detects signs of AF during a measurement the patient is notified via the watch and the app. The patient is instructed to then take up contact with our specialist nurse.

IkOefenZelf

Rehabilitation centre Basalt developed the portal “ikoefenzelf.nl” for online stroke rehabilitation. The goal of “ikoefenzelf.nl” is to implement the use of eRehabilitation and to give stroke patients the opportunity to practice where, when, and how often they want. More practice contributes to more participation and a better quality of life. The portal is

already used by at least 50% of all stroke patients in Basalt and offers stroke patients blended care applications for both physical and cognitive/mental training. After logging in to the portal using a hospital-provided, coded username and a password, patients can start their personal training, prepared for them by the rehabilitation professionals. The platform consists of education about stroke and the applications “Physitrack” (physiotherapy and occupational therapy), “MindDistrict” (psychology and social work), “Topwoordvinding” (speech therapy) and a time writing module (occupational therapy).¹⁹

StopAdvisor

The StopAdvisor app for support of smoking cessation has been developed by the Trimbos Institute, Pharos and NeLL, and is based on a scientifically proven intervention developed by the University College London. The StopAdvisor app is currently being used in collaboration with SineFuma, and will be made available to those patients participating in the pilot who smoke and are interested.

Coding the data

In general, the Withings connection-app requires an e-mail address, first name, last name, birth date and password for the patient in order to register himself. Without those details, the app cannot be used. Therefore, for privacy reasons, all patients receive a personal account. The key between the anonymous e-mail address of this account and the patient identity resides in the Electronic Medical Record (EPD-Vision). This procedure complies with LUMC requirements and has been approved by the LUMC security officer.

